## 2 ABBREVIATIONS and DEFINITIONS

ACT	Activated Clotting Time
AE	Adverse Event
AF	Atrial fibrillation
ASD	Atrial septal defect
AT	Atrial tachycardia
CABG	Coronary artery bypass graft (surgery)
CAD	Coronary artery disease
CBC	Complete blood count
CFAE	Complex fractionated atrial electrograms
CHADS 2	Scoring system in determining stroke risk for those with AF
CHA 2 DS 2 -VASc	Scoring system in determining stroke risk for those with AF (Congestive heartfailure, Hypertension, Age >75 years, Diabetes, Stroke/TIA, Vascular Disease, Age, Sex category
CIED	Cardiac implanted electronic device
CL	Cycle length
CRA	Clinical Research Associate
CRF	Case Report Form
CT	Computed tomography
CTI	Cavotricuspid isthmus
DMC	Data Monitoring Committee
EC	Ethics Committee
ECG	Electrocardiogram
EDC	Electronic Data Capture
GCP	Good Clinical Practice
HCG	Human chorionic gonadotrophin
HIPAA	Health Insurance Portability and Accountability Act
HRQL	Health Related Quality of Life, a subscale of the UFS-QOL
ICE	Intracardiac echocardiography
ICF	Informed consent form
ICH	International Conference on Harmonization
INR	International normalized ratio
LAA	Left atrial appendage
LMWH	Low-molecular-weight heparin
LV	Left ventricle
MI	Myocardial infarction
MRI	Magnetic resonance imaging
NYHA	New York Heart Association
PVI	Pulmonary vein isolation
RF	Radiofrequency
SADE	Serious Adverse Device Effect
SAE	Serious Adverse Event
TEE	Transesophageal echocardiography
TTE	Transthoracic echocardiography
TIA	Transient ischemic attack
UADE	Unanticipated Adverse Device Effect

### 3 BACKGROUND AND RATIONALE

Atrial fibrillation (AF) is the most common sustained arrhythmia in man, and has an increasing population prevalence over time. Treatment is aimed at stroke prevention on the one hand, and amelioration of symptoms (palpitations, lightheadedness, dyspnea, fatigue) due to the arrhythmia. Medical therapy often fails to render a satisfactory response for the latter, prompting the search for alternative therapies. Surgical and, in the last 15 years, catheter ablation techniques have been devised to try to prevent episodes from starting. Groundbreaking work by Haïssaguerre showed that premature discharges or rapid repeated firing from the pulmonary veins (PVs) could trigger AF episodes and that electrical isolation of the PVs could potentially cure the patient of AF. PV isolation currently is a painstaking process consisting of delivering radiofrequency energy or cryoablation in the left atrium to isolate these veins. Such procedures take 2-5 hr. to be completed depending on the complexity of the individual case, and a majority of patients require a 2nd or even 3rd procedure to achieve acceptable antiarrhythmic results. Despite considerable investigative effort, the exact pathophysiology of how PV triggers initiate and or maintain episodes of AF has been elusive.

Recently, a novel mapping technology (RhythmView, Abbott, Menlo Park, CA) based upon the work by Narayan et al has been developed for analyzing atrial recordings during human AF, finding that >95% of cases demonstrate either a rapidly spinning rotor (small circuit) or very rapid focal impulse formation. Furthermore, they have shown that catheter ablation at these relatively circumscribed areas can significantly affect AF, either by substantial slowing of the rate or termination (to an atrial tachycardia or sinus rhythm). In the CONFIRM (CONventional vs Focal Impulse and Rotor Modulation) trial, patients were treated with either conventional mapping and ablation (largely PV isolation or PVI) vs ablation of rotors or sites of focal impulse formation as designated by the mapping algorithm, followed by conventional ablation (PVI). The authors found much higher acute and long-term efficacy when focal impulse and rotor modulation (FIRM procedure) was used (82.4 vs 44% freedom from AF at 24 months post procedure). Although CONFIRM was a controlled study, a randomized evaluation would be warranted.

---

### 3.1 RATIONALE

According to the American Heart Association, atrial fibrillation affects approximately 2 million Americans. Atrial fibrillation may reduce cardiac performance and may result in thrombus formation in the left atrium and thromboembolic events, such as stroke. Approximately 15% of all strokes occur in people with atrial fibrillation. Ablation of atrial fibrillation that specifically targets approximately 2-5 mm outside of the pulmonary vein is currently a standard of care treatment in subjects with symptomatic atrial fibrillation who have failed drug therapy. Unfortunately, this procedure is time consuming, creates substantial damage in the left atrium due to the number of lesions required, and has mixed success with the best outcomes being 50-80% freedom from symptoms at 1 year post ablation. Also, as with any invasive procedure, patient complications may heighten with increased time and additional radiation exposure.

One of the major issues with the current procedure is the lack of knowledge about the critical regions of the heart that have the source rhythms causing and sustaining AF. Some very new technology developed based upon work done under NIH support at the University of California San Diego has shown promise in diagnosing these key source rhythms. Ablation to target these sources, called Focal Impulse and Rotor Modulation (FIRM) guided procedure, shows promise but need to be evaluated further.

### 3.2 HYPOTHESIS

Focal Impulse and Rotor Modulation (FIRM) guided procedures will eliminate the source of clinical arrhythmias in subjects with indications for AF ablation procedures.

## 4 **STUDY OBJECTIVES**

The primary objective is to compare the safety and effectiveness of FIRM-guided ablation procedures with conventional RF based pulmonary vein isolation ablation procedure for the treatment of paroxysmal atrial fibrillation (AF) for subjects without prior AF catheter ablation.

The secondary objective is to evaluate the treatment time and quality of life outcomes.

## 5 **STUDY DESIGN**

The study is designed as a prospective, multicenter, single-blind, randomized study to assess the safety and effectiveness of FIRM-guided RF ablation procedures for the treatment of symptomatic paroxysmal atrial fibrillation. The subjects will be blinded to study treatment for the duration of the study period.

### 5.1 SAMPLE SIZE

A total of 170 subjects at up to 15 investigative sites will be enrolled and equally (1:1) randomized between those undergoing conventional RF ablation with confirmation of PVI vs. those treated with FIRM-guided conventional RF ablation without PVI. Additionally, ablation of any atrial tachycardias (AT) and/or the cavotricuspid isthmus may be performed in those subjects with documented AT/atrial flutter.

### 5.2 RANDOMIZATION

Block randomization stratified by center will be used to assign subjects (1:1) to the conventional RF ablation treatment with PVI (PVI group), or to the FIRM-guided AF ablation procedure without PVI (FIRM group).

### 5.3 STUDY DURATION

Overall study duration (first subject enrolled through last subject exit) will be comprised of approximately 18 months of enrollment period. Study duration for an individual subject, once consented, will be up to 1 month for screening (including baseline measurements) and 12 months for follow-up after treatment for a total duration of approximately 13 months.

## 6 ENDPOINTS

### 6.1 PRIMARY EFFECTIVENESS ENDPOINT

Effectiveness endpoint is defined in the table below.

**Table 1 – Primary Effectiveness Endpoint**

Endpoint	Definition
Long term success	
Single-procedure freedom from AF/AT recurrence from 3-12 months post index ablation procedure (with 90-day blanking period).
 
* Freedom from AF/AT recurrence is defined as no documented episodes of AF/AT > 30 seconds with conventional non-invasive monitoring. In the case of a cardiac implanted electronic device (CIED), freedom from AF recurrence is defined as no documented episodes of AF/AT > 30 seconds in a 72-hour window at the follow-up visits in addition to any symptomatic episodes with documented AF > 30 seconds. AT recurrence does not include episodes of CTI (cavotricuspid isthmus) dependent flutter.

### 6.2 SECONDARY ENDPOINTS

Secondary endpoints are defined in Table 3 below. This study will also collect data relating to the health economics of the FIRM-guided procedure to conduct additional evaluations if primary endpoints are met.

**Table 2 – Secondary Endpoints**

Endpoint	Definition
Acute Effectiveness	

1. FIRM group: Elimination of identified AF rotors

2. Control group: Isolation of all pulmonary veins

Additional Secondary (unpowered) Effectiveness	
 
1) AF termination or CL prolongation, as identified by:           
 
a. Termination of spontaneous or induced AF by ablation of the source of arrhythmia.
 
b. Reduction of the mean AF rate by at least 10% by ablation of the source of arrhythmia.
 
 
 
2) Single-procedure freedom from AF/AT recurrence from 3-12 months post index ablation procedure (with 90-day blanking period) (Long-Term Effectiveness).
 
3) Freedom from symptomatic AF/AT recurrence from 3-12 months post index ablation procedure (with 90-day blanking period) (Long-Term Effectiveness).
 
4) Freedom from AF recurrence from 0-12 months post index ablation procedure (without 90-day blanking period) (Long-Term Effectiveness).
 
5) Freedom from AF recurrence at 12 months post index ablation procedure (can include repeat procedures).
 

Acute Safety Endpoint	
 
1. Freedom from procedure-related serious adverse events within 7 days of the procedure.
 

Long-Term Safe Endpoint	
 
1. Freedom from procedure-related serious adverse events within one year of the index procedure.
 

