**Table 5 – Intra-Procedure Guidelines**

Parameter	Description
-----------	-------------

Vascular access	Under sterile technique, the right and/or left femoral veins may be cannulated via Seldinger, or percutaneous approach. Other vascular access also may be obtained based upon physician judgment.
Reference catheter placement	Reference catheters (including 64-pole FIRMap catheter(s)) may be inserted and placed within the heart to record signals as clinically required at the discretion of the physician.
Access to left atrium	Access to the left atrium should be made according to the institution's standard practice.
Anticoagulation	Heparin should be administered per local protocol in order to achieve and maintain ACT > 300 prior to insertion of FIRMap catheter, if applicable. Heparin should be administered immediately following transeptal puncture in the case that ACT is not >300.
Catheter placement	Catheters may be inserted and used according to the institution's standard practice.
Source arrhythmia diagnosis	For FIRMap patients only: After obtaining at least 1 minute of continuous electrograms from the 64-pole FIRMap catheter either simultaneously or sequentially in the right and left atria, these electrogram data will be transferred to the RhythmView system. Right atrial mapping will initially be performed. If no right atrial rotor/source is detected or all right atrial rotors are eliminated, left atrial mapping will be performed. This will then produce FIRMap displays which will be interpreted by the operator to determine which locations have focal or rotor rhythms that could be sources of the AF.
3-D Electroanatomic Mapping	3-D electroanatomic maps may be created using CARTO (Biosense Webster, Johnson & Johnson) or Nav-X (St. Jude Medical) systems for documentation of anatomy and ablation lesion locations.
Induction of sustained AF	If the patient is not experiencing spontaneous, sustained AF (>5 min uninterrupted), induce sustained AF by atrial burst pacing from a catheter positioned within the CS or left atrial appendage until the atrial refractory period is reached or AF is induced with or without isoproterenol infusion.  IF AF CANNOT BE SUSTAINED, THE PATIENT DOES NOT MEET THE INCLUSION CRITERIA FOR THE PROTOCOL AND THE PATIENT WILL UNDERGO CONVENTIONAL AF ABLATION PER PHYSICIAN DISCRETION.

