Ablation data	For each ablation, the following data will be recorded: time, catheter size, lesion number, duration of application, average and maximum temperature.

FIRM-guided procedure	Under fluoroscopic guidance, a cardiac ablation catheter is passed to the location(s) identified as AF source rhythms (rotors or focal impulses). FIRM-guided ablation is performed at sites identified by the initial or repeated FIRMap. Such ablation typically consists of 3-5 minutes of ablation in the rotor core region followed by repeat mapping to confirm that the rotor has been eliminated. Following each FIRM guided site ablation, FIRMap is repeated and is followed by rotor ablation until all rotors are eliminated or AF terminates and remains noninducible. If AF terminates and is noninducible prior to repeat mapping, ablation of any identified and targeted rotor core region should be completed fully (e.g. ablation of the anatomic region with 3D electroanatomic guidance). In this FIRM-guided ablation arm, no PV isolation is performed. In case a rotor is located inside the PVs, focal ablation of the rotor (but no PVI) can be performed if the risk for PV stenosis is considered to be minimal as per discretion of the operator.
Conventional Ablation	Conventional ablation consists of isolation of all four pulmonary veins with confirmed entrance block assessed by a multipolar catheter.
Additional ablation for other arrhythmias (non-AF)	Additional ablation for other arrhythmias will be noted for atrial tachycardia (AT) and/or right cavo-tricuspid isthmus ablation in the event that the patient has documented AT/atrial flutter prior to or during the procedure.
ACT values	Activated Clotting Times (ACT) value is first measured prior to insertion of FIRMap catheter or trans-septal puncture, whichever comes first, to determine baseline value and then every 30 minutes post-heparinization until therapeutic and, subsequently, every 30 minutes during left-atrial access. (Heparin dosage should be adjusted to maintain ACT above 300 sec). The ACT will be monitored every 30 minutes following initial heparin delivery until the target value is achieved and subsequently checked at least every thirty minutes during the procedure.
Vascular access sheath removal	The vascular access sheaths will be removed according to the institutional standard.

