### C. *Intra-procedure Measurements*

The following data will be collected during the procedure. Table 6.

Data	Description
Fluoroscopy times	To be recorded: Total fluoroscopy time 
 
● The total fluoroscopy time for the procedure (a.k.a., "pedal down" time)
 

Total RF ablation time	Total RF ablation time as measured by total time of ablation lesion applications, from first ablation lesion to end of last lesion, will be documented. These values will be noted in both the FIRM-guided and conventional ablation groups. If ablation for AT/atrial flutter is pursued, this ablation time will be documented separately
Total procedure time	Total procedure time defined as: time from insertion of first sheaths for vascular access to removal of sheaths.
Medication administration	Cardiac medications administered during the procedure including drug name, dosage, and indication and will be recorded.
Devices and equipment	Devices and equipment used during the procedure including access devices, diagnostic and ablation catheters, and mapping equipment type will be recorded.

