#### E. Additional Secondary Investigations

Secondary Endpoints (unpowered) include:

1. AF termination or CL prolongation, as identified by:
  - a. Termination of spontaneous or induced AF by ablation of the source of arrhythmia.
  - b. Reduction of the mean AF rate by at least 10% by ablation of the source of arrhythmia.
2. Single-procedure freedom from AF/AT recurrence from 3-12 months post index ablation procedure (with 90-day blanking period) (Long-Term Effectiveness).
3. Freedom from symptomatic AF/AT recurrence from 3-12 months post index ablation procedure (with 90-day blanking period).
4. Freedom from AF recurrence from 0 – 12 months post index ablation procedure (without 90-day blanking period) (Long-Term Effectiveness).
5. Freedom from AF recurrence at 12 months post index ablation procedure (can include repeat procedures) (Long-Term Effectiveness).

Additional Investigations (unpowered) include:

1. Total RF ablation time.
2. Total Radiation Exposure.
3. Repeat ablation procedure and associated hospitalizations.
4. Quality of Life, as measured by the EQ-5D and AFEQT.
5. Cost-effectiveness analysis.

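### The AF-termination or cycle-length secondary endpoint has no PVI-arm definition, assessment time or listed data item, and the SAP's rate formula is actually a cycle length

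*Protocol*

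**What the plan says.** Protocol 6.2 Table 2 and 15.2 E, with SAP 1.2.1.5.1 and 2.3, list AF termination or cycle-length prolongation as a secondary endpoint. It has two components: "Termination of spontaneous or induced AF by ablation of the source of arrhythmia" and "Reduction of the mean AF rate by at least 10% by ablation of the source of arrhythmia". It stands under the label "Secondary Endpoints (unpowered) include", with no hypothesis, test or arm-specific wording.

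On sources, the diagnosis row of Protocol Table 5 opens "For FIRMap patients only". It has the operator read the FIRMap displays to "determine which locations have focal or rotor rhythms that could be sources of the AF". The conventional ablation row describes isolating the four pulmonary veins with confirmed entrance block and mentions no source.

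On data, the ablation row of Table 5 records, for each ablation, "time, catheter size, lesion number, duration of application, average and maximum temperature". Section 9.2 C, introduced by "The following data will be collected during the procedure", lists fluoroscopy, RF and procedure times, medication and devices. The schedule in Table 4 marks the AF symptom and rhythm assessment at baseline, discharge and follow-up, but not in the procedure column.

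On measurement, SAP 1.2.1.5.1 gives the mean AF rate as the total time of 10 consecutive coronary-sinus cycles divided by 10.

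**The concern.** Both components credit the effect to ablation of a source, and in this protocol that word belongs to the FIRM arm. Section 3.1 faults the current procedure for lacking knowledge of the source rhythms and presents FIRM as the way to target them. Section 3.2 says FIRM procedures will eliminate the source. A control subject whose AF stops during PVI may therefore not meet the definition as worded.

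The SAP files the endpoint under acute effectiveness, and SAP 3.1.3 plans an acute effectiveness table by treatment group. At stake is a displayed arm difference produced by the scoring rule and not by the procedures. The other acute effectiveness endpoint (Protocol 15.2 B) uses different success criteria in the two arms. This one could apply the same physiological measure to both, so it is worth defining properly.

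**Working it through.** The plan gives no rate, power or test for this endpoint, so there is no figure to reproduce. The check sets the texts side by side and adds two short calculations.

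**1. Is the PVI arm defined?** In Table 2, the acute effectiveness row has separate FIRM and control definitions. The row for this endpoint has one definition, built on the source. The FIRM-guided row of Table 5 equates AF source rhythms with rotors or focal impulses. No text states what the source is under PVI.

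**2. Is there an assessment time and a data item?** Table 4, the ablation row of Table 5 and section 9.2 C contain no entry for AF termination, AF rate or cycle length. Nothing says when the before and after values are taken, or how to score a subject no longer in AF at the second one. The SAP rule needs a coronary-sinus signal, while Table 5 leaves reference catheter placement to the physician.

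**3. What would a by-arm display show on the literal reading?** SAP 2.5 presents missing acute effectiveness data twice.
- Unscored controls excluded: the control denominator is empty and there is no comparator.
- Unscored controls counted as failures: the control rate is 0/85.

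For scale only, suppose someone applied the uncorrected chi-square that SAP 2.2.2 names for the other acute effectiveness endpoint, with 85 per arm and 4 FIRM successes against 0:
- Pooled proportion = 4/170 = 0.0235.
- z = (4/85) / sqrt(0.0235 × 0.9765 × 2/85) = 0.0471/0.0233 = 2.02, so chi-square is about 4.1 and p about 0.04.

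Four successes are also the minimum needed with 77 per arm. Under an assumed FIRM success rate, the simulated chance of reaching nominal significance is:

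| Assumed FIRM rate | 77 per arm | 85 per arm |
|---|---|---|
| 5% | 0.54 | 0.62 |
| 10% | 0.96 | 0.98 |
| 20% to 60% | about 1.00 | 1.00 |

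This would happen even if the arms did not truly differ. With only 4/2 = 2 expected successes per arm, the chi-square approximation is itself poor at that minimum.

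**4. Is the SAP rate formula right?** Total time divided by 10 cycles is a cycle length (CL). Rate per minute = 60,000/CL, with CL in ms. From an illustrative starting CL of 180 ms (333.3 per minute):
- 10% fall in rate: 0.9 × 333.3 = 300 per minute, so CL = 60,000/300 = 200 ms, a rise of 1/0.9 − 1 = 11.1%.
- 10% reduction of the SAP quantity, read literally: CL = 0.9 × 180 = 162 ms, so the rate is 60,000/162 = 370.4 per minute, a rise of 11.1%.

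The literal SAP criterion scores acceleration as success, which contradicts the endpoint's own title.

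**The case against.** A reader might infer that the endpoint cannot be scored under PVI and that the control result is 0 of 85 whatever happens. The documents do not support that. No text formally defines the source of arrhythmia as a FIRMap finding, and the restriction to FIRMap patients governs a mapping step. Protocol section 3 says firing from the pulmonary veins can trigger AF and that isolating them could cure it, so the veins can be read as the control-arm source. Inclusion criterion 7 requires sustained AF in every subject, so termination or slowing can be observed in both arms.

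A reader might also infer that the endpoint cannot be computed. That is not shown either. The eCRF is not among the documents. The list in 9.2 C is clearly not exhaustive: it also omits rotor elimination and PV isolation, on which the other acute effectiveness endpoint depends. In addition, the two alleged harms exclude each other. If neither arm has inputs, FIRM cannot come out ahead; if FIRM can be scored, its inputs exist.

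Finally, no between-arm test is planned here, and the table in SAP 3.1.3 may refer only to the rotor-elimination and PV-isolation endpoint, which shares the name.

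These points limit the concern without removing it. The looser reading is available but nowhere stated, and section 3.1 points the other way. A possible eCRF field does not supply an assessment time or a rule for subjects no longer in AF. The formula error does not depend on any of these points.

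**Conclusion.** The endpoint is under-specified; it is not impossible to score. It lacks an explicit PVI-arm definition, an assessment time and a listed data item, so a by-arm display cannot be interpreted until these are settled. The empty comparator or zero control rate follows only if three things hold: the source is read literally, the SAP 2.5 rule is applied to unscored controls, and this endpoint appears in the by-group table. The chi-square figures describe a test that the plan does not specify for this endpoint and show scale only.

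The SAP formula is wrong as written: it names a cycle length as a rate, which reverses the direction of success.

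The endpoint is secondary, unpowered and untested. Nothing here affects the primary effectiveness or safety conclusions. It is still worth correcting, because a cycle length not recorded at the procedure may not be reliably recoverable later.

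**What to change.** In Protocol Table 2 and 15.2 E, and in SAP 1.2.1.5.1 and 2.3, use one definition for both arms: AF termination, or a fall of at least 10% in AF rate, during the assigned index AF ablation (rotor or focal ablation, or PVI). Define AF rate as 60,000 divided by the mean coronary-sinus cycle length in ms over 10 consecutive cycles, and delete the present bracket.

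State how subjects no longer in AF at the second measurement are scored, and what is done when no coronary-sinus signal was recorded.

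List in section 9.2 C and the eCRF, for both arms, the rhythm and mean cycle length before the first and after the last AF lesion, and whether AF terminated.

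If the sponsor does not want to record this in controls, label the endpoint a FIRM-arm description and omit any by-arm display.

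The cost is a few extra data-entry fields per case and matching wording in both documents. A common definition will not remove one remaining asymmetry, which the report should mention: Table 5 makes AF termination part of the procedural end point in the FIRM arm, with no matching text for PVI.
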